4.6 USDA Mediterranean-style Food Pattern/ Medi for all

Participants randomized to the USDA Mediterranean-style Food Pattern Arm (called Medi for all) will have access to a "toolbox" that includes education materials (e.g., food pattern tables according to daily caloric intake), recipes, grocery lists, group-based online dietary support, feedback, and reminders to encourage dietary change. Recipes and grocery lists can be individualized to a participant's food budget and preferences. Materials will be available in print and Web-based. This state-of-the art intervention will then use electronic feedback in the form of nudge messages designed to motivate participants to sustain or improve adherence to the Med-style Food Pattern. Every two weeks, participants in the intervention arm will be prompted via a

digital online platform⁹⁶ (analog also available) to complete the 14-item Mediterranean Diet Assessment Score (an adapted version of the MEDAS Score¹⁴⁵ previously used in the PREDIMED34 study) for the purpose of providing timely, individual feedback on diet adherence (not for assessing adherence to the diet pattern). The MEDAS score will be calculated via the online digital platform and ranked according to 3 cutpoints: ≤ 7 , 8–9, or ≥ 10 .¹⁴⁵ Patients will be encouraged to achieve a score of ≥ 10 which is considered high adherence. The platform will then offer feedback based on the levels of self-reported adherence to the diet including self vs. peer comparisons and support resources. Nudge messages will utilize information from a baseline assessment of participants’ dietary attitudes and beliefs about which food groups within a Med-style food pattern they perceive to be most within their control. Ultimately, this approach will enable us to provide participants with dietary information and services that support adherence by accounting for attitudes, norms, and perceived control.¹⁴⁶⁻¹⁴⁸ The extent of interaction with the online platform will be assessed bi-weekly; degree of adherence to the USDA Med-style food pattern; and engagement in dietician services will be assessed at quarterly intervals.

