6.2 Clinical Complications

Death, SAEs, and complications (reported as AEs via EMR review) will be assessed and recorded through the study surveillance period. Complications (reported as AEs) will incorporate NSQIP standards and definitions as well as events related to antibiotic-related complications.

Table 3: Summary of SAE/AEs

| Serious Adverse Events | Adverse event |
|--|--|
| Death | |
| Life-threatening event | |
| CVA or stroke | |
| MI requiring treatment or cardiac arrest | Myocardial infarction Atrial arrhythmia |
| Unplanned admit to ICU | |
| Acute Renal Failure (requiring dialysis) | Major UTI (e.g., pyelonephritis) Urinary retention Acute Renal Failure (no dialysis) Progressive renal insufficiency |
| C. difficile colitis (requiring colon resection) | |
| Pulmonary embolism requiring therapy | DVT/PE requiring treatment |
| Coma >24 hours | |
| Septic shock (requiring pressors) | Sepsis |
| Bleeding requiring transfusion | |
| Newly infected prosthetic graft infection | |
| Mechanical ventilation >48 hours | Tracheal reintubation/tracheostomy |
| Colostomy or ileostomy | NG tube replacement (non-routine) Bowel obstruction Ileus |
| | Organ/space infection (including peritonitis) Surgical site infection Intra-ab Abscess Severe dehydration Hernia Malignant hyperthermia Pneumonia Other infection Other post-op occurrence: unspecified Other non-operative intervention: unspecified Unplanned (re)operative intervention during index C. difficile colitis (not requiring colon resect) |

| | |
|------------------------------|--|
| Other life threatening event | |
| Hospitalization* | |

*Exception to hospitalizations that do not need to be reported as an SAE:

- Planned, elective surgical procedures
- Labor and delivery
- Psychiatric hospitalizations

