9.0 Study Related SAEs

9.1 Identification of SAEs

Randomized participants will be monitored for SAEs throughout their study surveillance period (enrollment through twelve months). The occurrence of an SAE may come to the attention of study personnel during study follow-up phone interview or by a study participant calling the study team or presenting for medical care. Study staff will use the EMR to fill out the SAE form. The PI will then complete the form and sign the form. The SAE form will then be submitted to the DCC who will provide it to the ISM. The ISM will review the SAE form and ask the study team for additional clarification or specification as he/she sees necessary.

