9.2 SAE Reporting

Life-threatening complications or SAEs are a very rare possibility with both intervention arms. SAEs are defined as one of the following conditions (also listed in section 6.2.):

1. Death during the period of protocol-defined surveillance;
2. Life-threatening event related to the treatment or significant disability/incapacity related to the treatment; or
3. Inpatient hospitalization except for:
 - Planned, elective surgical procedures
 - Labor and delivery
 - Psychiatric hospitalizations

All SAEs will be:

1. Recorded on the appropriate SAE case report form;
2. Adjudicated by the ISM;
3. Followed until satisfactory resolution or until the study investigators deem the event to be chronic or the participant to be stable;
4. Reported to the study team and IRBs per their reporting guidelines; and
5. The study investigators will also report SAEs to the funder when appropriate.

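### The exemption of all psychiatric hospitalizations from SAE reporting is unqualified and unexplained, so an unplanned admission that meets no other SAE criterion gets no independent review

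*Combined protocol and SAP*

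**What the plan says.** Section 9.2 defines an SAE by three criteria. The first is "Death during the period of protocol-defined surveillance". The second is "Life-threatening event related to the treatment or significant disability/incapacity related to the treatment; or" and the third begins "Inpatient hospitalization except for", followed by three exceptions: elective surgery planned in advance, childbirth, and "Psychiatric hospitalizations". Section 6.2 carries the same three exceptions in the footnote to Table 3, under the words "Exception to hospitalizations that do not need to be reported as an SAE". That footnote hangs on the Hospitalization row only.

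Section 9.1 sets the route to the monitor: "The SAE form will then be submitted to the DCC who will provide it to the ISM". Section 9.2 has the ISM adjudicate SAEs, and section 9.3 has the ISM and the site lead decide whether an SAE is treatment-related.

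Section 4.6 describes the Medi for All arm. It combines educational materials, recipes, group support, a food-pattern score every two weeks, nudge messages, and feedback that includes "self vs. peer comparisons and support resources". Section 12.0 names no psychiatric risk from the intervention. The only psychological risk it mentions is discomfort or anxiety from questionnaires, which it expects to be low.

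**The concern.** The surgical exception is limited to operations that are both planned and elective, and childbirth is a defined event. The psychiatric exception has no limit. It covers planned and unplanned admissions, either arm, and any possible relation to the intervention, and neither section says why.

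Independent judgement of relatedness begins only once an event is an SAE. Exempting a whole class of admissions therefore settles the question for that class before any case is seen. The protocol itself presents Medi for All as partly a behavioural programme, and section 4.4 has no psychiatric or eating-disorder exclusion. At stake are the independent review of individual cases and the completeness of the SAE count by arm. No primary outcome and no planned estimate is affected.

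**Working it through.** The plan gives no figure to reproduce, so the check is mainly one of text.

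**Step 1. Is the exemption deliberate?** It appears in the same form in sections 6.2 and 9.2, so it is a consistent rule and not a slip.

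**Step 2. Which psychiatric events still qualify as SAEs?**

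| Event | Section 9.2 | Table 3 (section 6.2) |
|---|---|---|
| Death | SAE, any cause | SAE, any cause |
| Life-threatening event | SAE only if treatment-related | SAE with no relatedness condition (also "Other life threatening event") |
| Significant disability or incapacity | SAE only if treatment-related | Not listed |
| Unplanned ICU stay, coma over 24 hours, ventilation over 48 hours | Not listed separately | SAE with no relatedness condition |
| Psychiatric admission with none of the above | Exempt | Exempt |

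The gap is the last row, together with a disabling event that study staff have not already judged treatment-related. Sections 6.2 and 9.2 also differ on whether a life-threatening event must be treatment-related. The two should be reconciled, because the answer decides how much psychiatric harm is still captured.

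**Step 3. Does an exempt admission reach the ISM another way?**
- AEs are collected at 3, 6, 9 and 12 months (Table 1), self-reported ones are recorded (section 5.2.3), and section 8.5 tabulates AEs by group. Table 3's AE column has no psychiatric item.
- The Healthcare Utilization Form (section 5.3) can record a visit, but no text sends that form to the ISM.
- The ISM reviews patient-reported outcomes (section 8.8). DVQOL and GIQLI have emotional domains, but they are taken at baseline, 6 and 12 months and do not report admissions.
- Section 8.8 also provides for reports at 50%, 75% and full enrollment, but does not say that they contain exempt admissions.

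No stated route brings the individual case to the ISM.

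**Step 4. Scale.** The documents give no psychiatric admission rate. Assume a 12-month risk *r* per participant from any cause. The sizes, from section 8.7, are *n* = 75 in total and *n* = 50 in the Medi for All arm. The expected number is *n* × *r*, and the chance of at least one is 1 − (1 − *r*)^*n*, counting each participant once.

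| Assumed *r* | Expected in 75 | At least one in 75 | Expected in 50 | At least one in 50 |
|---|---|---|---|---|
| 0.2% | 0.15 | 14% | 0.10 | 10% |
| 0.5% | 0.375 | 31% | 0.25 | 22% |
| 1% | 0.75 | 53% | 0.50 | 39% |

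These are background admissions from any cause. They are not the chance of an admission caused by the intervention.

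**The case against.** The strongest reply is that this is a consistent definition in a study that section 8.8 calls minimal risk, and that the worst outcomes are already covered. Much of that stands. Death is an SAE whatever its cause, and Table 3 keeps life-threatening events, unplanned ICU stays and similar items with no psychiatric exception. A medical, non-psychiatric admission after self-harm falls outside the exemption's wording. Exemption from SAE reporting is also not exemption from AE recording.

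A reader might infer two stronger claims, and the documents support neither. The first is that nudges and peer comparison about eating could cause psychiatric harm. Nothing in the protocol says so. The two-weekly tool scores a 14-item food pattern, peer comparison is one element of a programme with many parts, and section 12.0 names no such risk. The second is that serious psychiatric harm does not reach the monitor at all. Step 2 shows that the fatal and life-threatening end does, at least under Table 3.

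What remains is narrower. An unplanned admission below those thresholds has no stated path to independent review. Minimal-risk status lowers the urgency, but it does not explain why this one class is exempt without limit.

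**Conclusion.** The point holds in limited form. As written, an unplanned psychiatric admission that is not fatal, life-threatening, or disabling and treatment-related generates no SAE form. The ISM does not adjudicate it or assess its relatedness, and the SAE count omits it in both arms. It may still appear among the AEs.

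This rests on the wording of sections 6.2 and 9.1 to 9.3, and needs no assumption about what the intervention causes. Only the scale rests on an assumption: at a 0.2% to 1% annual risk, fewer than one such admission is expected in the whole trial. That is too few for any comparison between arms, so the matter is oversight of individual cases. Priority is minor.

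**What to change.** In the Table 3 footnote (section 6.2) and in section 9.2, restrict the psychiatric exception to planned admissions, in parallel with the surgical exception. Unplanned psychiatric admissions would then be recorded on the SAE form, adjudicated by the ISM and tabulated by arm like other hospitalizations. Deleting the line altogether would go further than needed, because planned psychiatric admissions would become SAEs too. If the sponsor prefers to keep the full exemption, the protocol should give the reason and say how a possibly related admission reaches the ISM. The same amendment can align sections 6.2 and 9.2 on life-threatening events.

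The cost is one changed line in each of two lists, probably zero or one extra SAE form (0.15 to 0.75 expected under the assumed rates), and care in handling sensitive records.

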9.3 Assignment of SAEs as Treatment Related

The determination of whether an SAE is related to the treatment will be assessed by the ISM and site lead, based on supporting documentation provided by the research coordinators case reports or in consultation with the treating physician, as needed.

10.0 Reporting Procedures

SAEs will be captured on the appropriate source document. Information to be collected includes event description, date event occurred, date study personnel became aware of the event, investigator assessment of event severity, event outcome, and relationship to study treatment. All SAEs will also have information on action taken at time of report, date SAE resolved, outcome at time of SAE report, and, depending on the site, whether the IRB has been notified.

For SAEs, the date of resolution (or when the event is deemed stable/chronic) will be noted on the appropriate case report form.

11.0 Protocol Violations and Deviations

A protocol violation is any non-compliance with the clinical trial protocol or Good Clinical Practices. The noncompliance may be either on the part of the participant, the investigator, or the study site staff and most often is related to study enrollment. Anticipated protocol violations

are 1) Participant enrolled but did not meet inclusion criteria, 2) Participant enrolled but exclusion criteria present or eligibility criteria not met, 3) Consent not obtained in accordance with IRB guidelines, 4) Randomization failure

A protocol deviation is a smaller digression from study protocol. Deviations are monitored with consideration for protocol amendment should it become clear that the original protocol was too inflexible.

It is the responsibility of the research staff to use continuous vigilance to identify and report violations and deviations within 5 working days of identification of the protocol violation/deviation.

All violations and deviations from the protocol will be addressed in study participant source documents. A completed copy of the Protocol Violations and Deviation Form will be maintained in the regulatory file, as well as in the participant's study chart. Protocol violations and deviations will be sent to the local IRB per their guidelines. The study staff will be responsible for knowing and adhering to their IRB requirements.

12.0 Protection of Human Participants

We expect that most patients will have good baseline health but will not exclude patients with most stable and chronic medical conditions, other than those characteristics described in the exclusion criteria.

Patients of childbearing potential will be excluded if they have a positive pregnancy test documented prior to enrollment. Incarcerated patients will be excluded. There is no evidence from prior studies to suggest there will be differences in intervention effect among sex/gender or racial/ethnic subgroups.

The risks and benefits for participants enrolled in this trial are appropriately balanced and minimal. The primary risks of this study are loss of patient privacy, loss of confidentiality, study burden, and risk of bleeding, bruising, or discomfort during the specimen collection.

Loss of confidentiality could occur if the study database were breached. This risk will be low because of numerous steps to protect confidentiality. Approaching patients about enrollment in the clinic poses a risk to privacy. We anticipate this risk to be low. Patients will be approached in a private clinic room. To avoid threats of coercion, providers will be educated but not directly involved with recruitment of patients. We expect the risks of discomfort or anxiety related to study questionnaires to be low. There is a small risk of bleeding, bruising, or discomfort at the site of the blood collection. Attention will be taken to apply pressure following the procedure to reduce bleeding. There is also a small risk of fainting or feeling faint during a blood draw. There is minimal discomfort associated with collection of the fecal (stool) sample. We expect these specimen collection risks to be low.

Study participants could benefit from participation in this study by learning how to increase their dietary fiber intake or how to integrate tools from the Medi For All diet and behavioral intervention, potentially helping their diverticulitis symptoms.

Informed consent is a process that is initiated prior to the individual's agreeing to participate in the study and continuing throughout the individual's study participation. Extensive discussion of risks and possible benefits of both interventions will be provided to the participants using standardized materials. Consent forms describing in detail the study procedures and risks will be given to the participant and documentation of informed consent will be required prior to completing study assessments.

Consent forms will be IRB-approved and the participant will be given sufficient time to read and review the document. They will be specifically asked if they have any questions or concerns, which will be addressed, or would like more time to consider their participation, which will also be provided. The study team will explain the research study to the participant and answer any questions that may arise. The participants will sign the informed consent prior to completing any study related activities. The participants may withdraw consent at any time throughout the course of the study. A copy of the informed consent will be given to the participants for their records. The rights and welfare of the participants will be protected by emphasizing to them that they will still be able to receive medical care at the facility if they decline to participate in this study.

Participant confidentiality is strictly held in trust by the participating investigators and their staff.

